TITLE

Occult Paroxysmal Atrial Fibrillation in Non-Cryptogenic Ischemic Stroke

PRINCIPAL INVESTIGATOR:

[name]

CO-INVESTIGATORS:

[name], [name], [name], [name], [name]

CAMPUS:

North Shore University Hospital

INTRODUCTION/BACKGROUND MATERIAL/PRELIMINARY STUDIES AND SIGNIFICANCE

Atrial Fibrillation (AF) is an independent risk factor for stroke.¹ Between 50 and 59 years of age, 1.5% of strokes are attributed to AF, but between 80 and 89 years of age the proportion increases to 23.5%. There are 15 strokes every hour from AF.

Paroxysmal AF (PAF) is sporadic, asymptomatic and has similar risk of stroke when compared to continuous AF.^{2,3} It is not clearly defined in the literature and is more prevalent than persistent AF in patients with ischemic stroke and TIA.⁴ The incidence of paroxysmal AF in cryptogenic stroke is 1 in 6 for age > 55 and 1 in 5 for age > 75.⁵ Most studies based on the prevalence of stroke in the US would suggest that approximately 200,000 individuals may have ischemic stroke associated with PAF. We suspect this number to be higher since long-term monitoring has been restricted only to the cryptogenic stroke population. The risk of stroke recurrence is four times greater among stroke patients with newly detected AF (15.5%) compared to those with either known AF or no AF (3.9%).⁶ Some studies have shown that 5% to 30% of cryptogenic strokes may be due to undetected AF.^{7,8}

The standard Holter monitor has a low sensitivity for detecting paroxysmal AF following an ischemic stroke (approximately 5%). In the recent Crystal AF study, 30% of cryptogenic stroke patients randomized to the Reveal Insertable Cardiac Monitor were found to have PAF compared to 3% of controls over a 3 year monitoring period.^{8,9} There are numerous observational studies that support greater detection of AF with longer monitoring. (Table 1)^{10,11} Median time to AF episode detection was 84 days. Prior studies have shown that long term monitoring for detection of PAF is cost effective.¹² While the relatively high incidence of silent PAF in cryptogenic stroke patients is just now being elucidated, there is no understanding of the frequency of silent PAF in patients with a “known” or presumed etiology for their ischemic stroke other than AF. If this incidence were also found to be significant, a dramatic change in stroke evaluation and management would likely occur.

Anticoagulation is the treatment of choice for AF and paroxysmal AF.¹³ Anticoagulation in patients with paroxysmal or chronic AF reduces the risk of stroke by 64% and death by 25%.⁵ The identification of paroxysmal AF in EMBRACE (30 day) and SURPRISE (mean 133 days) led to a change in management to full anticoagulation in 13% and 18% of patients, respectively. In the Crystal AF study, 97% of patients who were diagnosed with AF were changed to oral anticoagulants.⁸ It is postulated that in the era of the novel oral anticoagulants, the detection of AF and the appropriate initiation of anticoagulation as secondary stroke prevention will reduce the risk of recurrent ischemic stroke without increasing the rates of symptomatic intracerebral hemorrhage or systemic hemorrhage. For patients with a presumed stroke mechanism other than AF who are found to have silent PAF, a change in management to full anticoagulation could have similar effects.

OBJECTIVE(S)/SPECIFIC AIMS AND HYPOTHESES

Primary Objective:

To determine the incidence of paroxysmal atrial fibrillation (AF) in ischemic stroke patients who have a presumed known stroke etiology other than atrial fibrillation.

Secondary Objectives:

- 1. Percentage of patients who are diagnosed with AF who are changed to anticoagulant therapy.**
- 2. Duration and frequency of AF episodes.**
- 3. Percentage of asymptomatic AF episodes.**
- 4. Incidence of recurrent ischemic stroke.**

SUBJECT SELECTION – ELIGIBILITY CRITERIA

The subject population will include patients with a diagnosis of Ischemic stroke. A total of 75 patients will be enrolled over a **2-year period**.

Inclusion Criteria:

Patients with a recent ischemic stroke or TIA with brain infarction on brain imaging.

1. No history of atrial fibrillation or finding of atrial fibrillation on standard inpatient monitoring (ECG, telemetry, 24-hour Holter monitor)
2. Have a presumed stroke etiology: Lacunar or small vessel thrombosis, extra-cranial or intracranial atherosclerotic stenosis or dissection, arteriopathy or vasculitis, hypercoagulable state, aortic arch plaque with or without mobile elements, or evidence of a low-risk cardiac source (e.g., PFO with or without atrial septal aneurysm and with or without evidence of venous thromboembolic source).

The following diagnostic tests are minimally required to determine the stroke etiology:

- Brain MRI
- 12-lead ECG for AF detection

- 24-h ECG monitoring for AF detection (eg, Holter monitor or cardiac telemetry)
- TTE and/or TEE
- CTA or MRA of head and neck
- Hypercoagulable blood panel for patients less than 55 years-old
 - Preliminary hypercoagulable work-up within 7 days will include the antiphospholipid antibody syndrome results, which will be needed to determine stroke management. All other results, which could take longer to return, including genetic tests of hypercoagulability, rarely change stroke management.

1. Have virtual CHADS2 score ≥ 3 , or
2. Have 2 or more of the following co-morbidities: obstructive sleep apnea, coronary artery disease, (Chronic Pulmonary Obstructive Disease (COPD), hyperthyroidism, BMI > 30, prior MI, prolonged PR interval (>175 ms) or renal impairment (GFR 30-60).
3. Patient or legally authorized representative who is willing to sign written consent form.
4. Patient is ≥ 40 years old (patients younger than 40 years old have a very low likelihood of having atrial fibrillation and are therefore excluded from the study).
5. Patient can have the device implanted within 10 days of the incident ischemic event

Exclusion Criteria:

1. Documented history of AF or atrial flutter.
2. Evidence of a high-risk cardiac source of embolism (LV or LA thrombus or “smoke,” emboligenic valvular lesion or tumor)
3. Untreated hyperthyroidism.
4. Myocardial infarction or coronary bypass grafting within 1 month prior to the stroke/TIA.
5. Valvular disease requiring immediate surgical intervention.
6. Permanent indication for anticoagulation at enrollment.
7. Permanent oral anticoagulation contraindication.
8. Already included in another clinical trial that will affect the objectives of this study.
9. Life expectancy is less than 1 year.
10. Pregnancy. Urine or serum pregnancy test is required for women of child bearing potential to exclude pregnancy.
11. Patient is indicated for implant with a pacemaker, ICD, CRT device, or an implantable hemodynamic monitoring system
12. Patient is not fit, or is unable or unwilling to follow the required procedures of the Clinical Investigation Plan.
13. Cryptogenic Stroke: A stroke/TIA will be considered cryptogenic if no cause is determined despite extensive inpatient workup (see Inclusion criteria) according to the standard diagnostic protocol at North Shore University Hospital

DESIGN:

This is a single center prospective, non-blinded, cohort study that will be conducted over a period of 3 years (2 year patient enrollment and a minimum of 12 months of ICM monitoring). Patients will be evaluated according to standard institutional stroke/TIA clinical guidelines. Participants will be recruited within 7 days after the diagnosis of a stroke once diagnostic tests have been completed and a presumed stroke etiology has been identified.

All eligible patients will be approached for an informed consent to participate in the study. The primary goal of the study is to detect paroxysmal atrial fibrillation (AF) in ischemic stroke patients who have a presumed or known stroke etiology other than AF. The detection of paroxysmal AF will very likely lead to a change in their secondary stroke prevention strategy.

Stroke or TIA is considered to be cryptogenic if no stroke mechanism can be determined after an evaluation according to the standards of American and European Guidelines. Such patients will be excluded from the study.

Reveal LINQ Insertable Cardiac Monitor:

The LINQ ICM (Medtronic, Inc.; See photo in Appendix B) is a small cardiac monitor implanted in the subcutaneous tissue of the chest wall that is designed to continuously record a single-lead ECG, monitoring the cardiac rhythm for up to three years. A previous study of a similar device (Reveal XT ICM; Medtronic, Inc.) has demonstrated the technology’s ability to correctly identify AF in 96.1% of patients and to correctly exclude AF in 97.4% of patients. The LINQ ICM (or future iterations) will be utilized in this study to detect occult paroxysmal AF in our study population. The LINQ ICM is approved by the FDA for use in patients where there is a suspicion of occult cardiac arrhythmias and is therefore being utilized in this study in accordance with the FDA labeling.

The LINQ device is 87 % smaller than the Reveal device. It is pre-loaded in the insertion tool. The size of the device is 1.2 cc and it is interrogated using external equipment. It is able to store 4 separate patient activated events in the electrogram.

EP Cardiology, directed by [name], will be implanting the device and have been trained by the manufacturer of the device. The cardiologists have been implanting similar devices for several years and have been trained on this specific device since February 2014. The insertion procedure involves draping the patient followed by local anesthesia at the site of implant. This is done under sterile precautions. A small incision is made under local anesthesia. Electrocautery to achieve hemostatis is rarely required. The device is then inserted using the insertion tool provided in the device kit. There is a risk of local site bleeding, infection, device migration, allergy to the device component, cosmetic complications from incision and inability of the device to capture some particular arrhythmias.

The best location of insertion of the device is 45 degrees relative to sternum over the 4th intercostals space (V2-V3) electrode orientation. This assures good signal quality. The second best option is 4th intercostals space approximately 2 cm parallel to the edge of sternum. If the above-recommended locations are not suitable, optional locations must be considered. The device is compatible with mammography and MRI (1.5T and 3T magnets). For precautions related to these procedures please refer to Reveal LINQ ICM Medical Procedure Manual (to be attached to this document.)

LINQ settings for high sensitivity and specificity will be set to:

o AF only – All Episodes

-The device will store all AF episodes that are irregular. Capture of these episodes is not based on the ventricular rate, it is based on irregularity.

- Stored episodes are representative of the first two minutes of each episodes

- Device will store approximately 13 episodes of 2 minutes duration (max 27 minutes)

o Balanced Sensitivity

o Ectopic Rejection: Aggressive

Follow Up:

Device recording of an AF episode of at least 2 minute duration will be required to diagnose a patient with AF. A partial device transmission (summary of potential AF episodes) will be automatically downloaded daily via the Medtronic MyCareLink patient monitor and the study cardiologist will receive an alert within 24-48 hours if the computer monitoring system confirms an episode to be probable AF. Participants may also use the Reveal Patient Assistant to activate recording of cardiac information in the Reveal LINQ ICM while experiencing or immediately after a symptomatic event. Participants will be required to perform a manual device interrogation on a monthly basis. All downloaded rhythms will be manually reviewed every month for each enrolled patient by the study cardiologist. Each AF episode will also be independently adjudicated by a cardiologist blinded to the study protocol.

A total of 75 patients will be enrolled in the study. After enrollment, patients will have study visits at 1, 6, and 12 months. Six and 12 month follow-up visits will be conducted at these time intervals plus or minus 30 days. If the patient cannot come in for a follow-up visit, then the follow-up may be performed as a telephone interview. During the study visits, patients will be assessed for any interval stroke or TIA-like events, intracerebral hemorrhages, interval medical history, device related complications or other adverse events. At the 1-month visit, a NIH stroke scale score will be obtained. At each study visit, a modified Rankin score will be recorded. There will not be any research labs conducted at these study visits and only blood work associated with routine care may be obtained.

Patients will also have one EP cardiology clinical follow-up visit 10 days (plus or minus 4 days) after device implantation to ensure proper healing of the surgical site and functioning of the device.

At the completion of the study, if there is no clinical reason not to remove the device, then the device will be removed at 1 year from implantation. If there is a clinical indication for longer monitoring, then the device will be kept in longer for a maximum of 3 years. However, if clinical monitoring is required beyond the study period, then monitoring will be performed outside of the

study, and the patient or the patient's insurance will be responsible for any clinical fees associated with this post study monitoring.

At the conclusion of the study, Drs. [name] or [name] will be primarily responsible for removing the device; however, they may appoint one of their colleagues as designee to remove the device if they are unavailable.

INFORMED CONSENT

Subjects meeting the above inclusion/exclusion criteria will be approached by a study physician investigator and invited to participate in the study. If the patient agrees the study investigator will guide the patient through the informed consent process. All enrollees will undergo a detailed informed consent process during which risks, benefits and alternatives of participation will be discussed.

In the case of diminished or altered capacity, the assessment of the subject's decision making capacity will be made by the treating Stroke Neurologist. If the subject is deemed incapable of making his or her own health-care decision, a legally authorized representative (LAR) may be assigned. If the patient is awake, alert, and oriented and demonstrates appropriate cognitive and communicative abilities as determined by the interviewing/treating physician, the patient will be deemed to have the appropriate capacity to consent, as defined in the North Shore University Hospital Policies and Procedures Manual, Informed Consent, Policy No. 100.23, Pg 3.

If the patient is deemed not to have the appropriate capacity to consent at the time of interview and a next of kin (NOK; spouse, adult child, parent, adult sibling, other relative) is available, that individual will be deemed the LAR (see North Shore University Hospital Policies and Procedures Manual, Informed Consent, Policy No. 100.23, Pg 4). Deeming a NOK as the LAR is necessary since stroke patients frequently lack capacity immediately following a stroke and because these patients are at high risk of recurrent stroke. This risk is especially high and relevant for patients who have undiagnosed atrial fibrillation, and who, therefore, would not be on appropriate antithrombotic therapy for secondary stroke prevention.

If the patient's decisional capacity is impaired, but the treating Stroke Neurologist deems the patient capable of assenting to study participation, then the patient and their LAR will be included in the informed consent process. In this case, enrollment will proceed only if the patient assents and the LAR gives consent to study enrollment. In the event that the participant is decisionally impaired to the point where both consent and assent cannot be obtained for the study, consent will be obtained from the LAR. In any other situation where the patient is deemed not to have the capacity to consent, the decision will be made not to enroll the patient in the study. All clarifications will be handled directly by the principal investigator.

The use of an LAR will be documented on the data collection form. Enrollment into the study after the informed consent process is completed will be documented in the medical record. In the event that an LAR consents on behalf of a patient lacking capacity, continuing informed consent will be obtained if the treating physician or study physician determines that the patient regains the capacity to consent during the course of the protocol. Assessment for regaining capacity to participate in the informed consent process will be performed at each study visit.

STATISTICAL ANALYSIS

Descriptive statistics (mean \pm standard deviation and median for continuous data such as age; frequencies and percentages for categorical data such as gender, medical history, etc) will be calculated for baseline patient characteristics.

The incidence of AF will be calculated as the total number of patients with AF in 12 months divided by the total number of patients studied, along with the corresponding 95% confidence interval.

The analysis of “time-to-first-documented-AF” will be accomplished by applying standard methods of survival analysis, i.e., computing the Kaplan-Meier¹ product limit curves. In cases where the endpoint event, “AF”, had not yet occurred, 12 months will be used and considered ‘censored’. The median rate will be obtained from the Kaplan-Meier/Product-Limit Estimates and its corresponding 95% confidence interval will be computed, using Greenwood’s formula² to calculate the standard error.

Univariate analyses will be performed to screen for potential predictors of AF. The chi-square test or Fisher’s exact test, as deemed appropriate, will be used to compare AF patients with non-AF patients for categorical variables and the two-sample t-test or Mann-Whitney test for continuous data.

As a possible secondary analysis, those factors that appear to be associated with AF in the univariate analysis ($p < 0.25$) will be included in a logistic regression model. Backwards selection will be used to remove variables that do not significantly contribute information to the model, given other factors included in the model. A receiver operating characteristic (ROC) curve will be constructed to look at the final model’s ability to predict AF. A numerical measure of the accuracy of the model will be obtained from the area under the curve (AUC), where an area of 1.0 signifies near perfect accuracy, while an area of less than 0.5 indicates that the model is worse than just flipping a coin. The following will be used as a guide for AUC:

0.9-1.0	Excellent
0.8-0.9	Very good
0.7-0.8	Good
0.6-0.7	Average
0.5-0.6	Poor

The Hosmer and Lemeshow Goodness-of-Fit test will also be used to test how well the model fits the data.

Unless otherwise specified, a result will be considered statistically significant at the $p < 0.05$ level of significance. All analyses will be performed using SAS (SAS Institute, Cary, NC).

DISCOMFORTS AND RISKS

The risks to the subjects are low in relation to the anticipated benefits of detecting paroxysmal AF, which will change the strategy of secondary stroke prevention from antiplatelet to anticoagulation

¹ Lee, E. T. (1992), *Statistical Methods for Survival Data Analysis*, Second Edition, New York: John Wiley & Sons.

² Greenwood M. (1926), *The Errors of Sampling of the Survivorship Table*, Vol. 33 of Reports on Public Health and Medical Subjects. London: Her Majesty’s Stationery Office

therapy and reduce the annual risk of recurrent stroke by allowing earlier treatment once AF is detected. The procedural risks have been reviewed under the section (“Design: Reveal LINQ Insertable Cardiac Monitor)

Potential risks and discomforts associated with receiving a Reveal LINQ ICM device include:

- Local site bleeding
- Temporary discomfort at the implant site.
- Rejection of the device by the body, which may have symptoms such as swelling, redness, or other irritation at or near the implant site
- Movement of the device from its original implant location
- Allergy reactions to the device
- Infection at the site of the implant
- Cosmetic complications at the site of device placement
- Inability of the device to capture some particular arrhythmias
- Risks associated with local anesthesia, including hypersensitivity and allergic reactions to the anesthetic agent, injection site bleeding or infection

POTENTIAL BENEFITS

The presence of paroxysmal AF in non-cryptogenic stroke patients, who have a presumed stroke etiology other than AF, will help in identifying a stroke etiology that carries a high risk for recurrent stroke and will most likely result in a significant management adjustment in terms of long-term anticoagulation for secondary stroke prevention. It is well accepted that long-term anticoagulation of ischemic stroke and TIA patients with paroxysmal AF decreases the incidence of recurrent stroke.

DISCONTINUATION OF STUDY/SUBJECT WITHDRAWAL

Subjects have the right to withdraw from the study at any time without prejudice. The site investigator may withdraw the subject from the study and remove the implantable device in the event of intercurrent illness, adverse events, other reasons concerning the health or well-being of the subject, or in the case of lack of cooperation, non-compliance, protocol violation or other administrative reasons. Participants who regain decisional capacity and do not want the device in their body will also be withdrawn from the study and the implantable device will be removed. This will be discussed in detail during the enrollment and consenting process.

DATA AND SAFETY MONITORING

The Principal Investigator will be tasked with ensuring the data and safety of the study. This review will occur every 6 months after the first subject is enrolled. The PI, along designated co-investigators, will review the incoming data to determine if aspects of the study need to be changed or stopped. In addition, they will review any and all deviations, adverse events and unanticipated problems that may occur to determine their relatedness to the study, their severity, and whether they require study changes. Adverse events include any device related complications or interval new medical conditions. Adverse events will be considered severe if they require hospitalization or are life threatening, or result from a malfunctioning of the study device. In addition, any unanticipated problems will be reported to the IRB and the LINQ manufacturer as per their specific reporting requirements.

CONFIDENTIALITY

The data will be collected and stored on the “shared drive” that can be accessed by the investigators and research coordinators through a login and password on the NSLIJHS server. All PHI will be de-identified in the data set and will not be shared with any outside facility.

FUNDING

Funding for this research study is provided by Medtronic, Inc. The funding is used to support the activities of the Departments of Neurology and Cardiology to pay back the Departments for the costs of the study personnel. Medtronic may potentially donate up to 10 Reveal LINQ devices if the patient need arises. However, Medtronic is not donating all of the devices for this study. As the Reveal LINQ device is being used within its FDA indications, the charge for the device will be billed to the patient’s insurance carrier.

REFERENCES:

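### Does the primary objective promise an AF incidence for all non-cryptogenic stroke when only patients aged 40 or more with added risk factors are enrolled?

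*Combined protocol and SAP*

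**What the plan says.** The protocol with its statistical section is a single document. Under OBJECTIVE(S)/SPECIFIC AIMS AND HYPOTHESES the primary objective reads "To determine the incidence of paroxysmal atrial fibrillation (AF) in ischemic stroke patients who have a presumed known stroke etiology other than atrial fibrillation". DESIGN repeats the goal in equally general terms, and the title is "Occult Paroxysmal Atrial Fibrillation in Non-Cryptogenic Ischemic Stroke".

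The inclusion criteria under SUBJECT SELECTION are narrower. Besides a presumed etiology, a patient must satisfy one of two risk conditions: "Have virtual CHADS2 score" of at least 3, or "Have 2 or more of the following co-morbidities: obstructive sleep apnea, coronary artery disease" and others on a list. The minimum age is 40, with the reason given: "patients younger than 40 years old have a very low likelihood of having atrial fibrillation and are therefore excluded from the study". Thirteen exclusions follow.

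STATISTICAL ANALYSIS defines the primary estimate as the "total number of patients with AF in 12 months divided by the total number of patients studied", with a 95% confidence interval.

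**The concern.** The main result of this single-arm study is one absolute proportion. With no comparator, selecting patients on their risk of the outcome acts directly on the headline number. The age floor is explicitly such a selection, and the CHADS2 or co-morbidity condition plausibly works the same way.

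Nothing in the analysis section carries the estimate back to the wider population. There is no weighting or standardisation, and the predictor analyses compare enrolled patients only. The confidence interval covers sampling error alone.

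The introduction also attaches weight to the result: "If this incidence were also found to be significant, a dramatic change in stroke evaluation and management would likely occur". If the proportion were read as the incidence in all non-cryptogenic stroke, it could be applied to patients under 40 or without the risk condition, for whom the study collects no monitoring data.

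**Working it through.** **Is there a figure to reproduce?** No. The target of 75 patients is stated without an assumed AF rate or precision, so no calculation in the plan depends on which population is meant.

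**Side-by-side reading.** The restart of the numbering in the inclusion list is read so that the word *or* joins only the CHADS2 and co-morbidity items.

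| Element | Objective and DESIGN | Eligibility | Primary estimate |
|---|---|---|---|
| Etiology | presumed, not AF | same | as enrolled |
| Age | no limit | 40 or more | as enrolled |
| Risk | no limit | CHADS2 at least 3, or two or more co-morbidities | as enrolled |

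The objective is broader than the cohort. The estimator agrees with the eligibility list.

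**What the difference would amount to.** Let f be the share of the wider population that meets the age and risk conditions, pE the incidence in that share and pI the incidence in the rest.

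- Incidence in the wider population = f × pE + (1 − f) × pI
- The study estimates pE, so the gap is pE minus that quantity = (1 − f)(pE − pI)

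None of f, pE and pI is in the documents. As an illustration only, assume pE = 20%:

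| Assumed f | Gap if pI = 10% | Gap if pI = 5% |
|---|---|---|
| 0.3 | 0.7 × 10 = 7.0 points | 0.7 × 15 = 10.5 points |
| 0.5 | 0.5 × 10 = 5.0 points | 0.5 × 15 = 7.5 points |
| 0.7 | 0.3 × 10 = 3.0 points | 0.3 × 15 = 4.5 points |
| 0.9 | 0.1 × 10 = 1.0 point | 0.1 × 15 = 1.5 points |

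For scale, 15 of 75 patients is 20.0%, with an exact 95% interval of 11.6% to 30.8%. Read as an interval for the wider population, it would cover the true value 68% of the time at f = 0.3 and pI = 10%, 24% at f = 0.3 and pI = 5%, and 96% at f = 0.9 under either pI. For the enrolled population it has its ordinary meaning.

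**Direction.** The protocol's own reason for the age floor implies an upward shift from that criterion. For the risk condition no reason is given, and the virtual score is not defined, so its restrictiveness cannot be judged. Exclusions 2, 3, 4 and 11 (high-risk cardiac source, untreated hyperthyroidism, recent infarction or bypass surgery, device indication) may pull the other way. The net sign is not established.

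**The age figures in the introduction.** They state that at 50 to 59 years "1.5% of strokes are attributed to AF, but between 80 and 89 years of age the proportion increases to 23.5" percent. Both bands lie above the age floor, and the figures concern strokes attributed to AF, not occult AF in non-cryptogenic stroke. They cannot size the effect of excluding patients under 40.

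**What rewording would alter.** With the age and risk limits written into the objective, the estimator, the 75 patients, the interval and the 12-month follow-up are all unchanged.

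**The case for a change.** The strongest case for acting is that this is more than the usual shortening of an objective. The selection is tied to the outcome, the result is an absolute rate with no control group, and the introduction anticipates a change in practice. Restating the objective would cost little, and a count of patients turned away by the age or risk rule would show how selected the cohort is and may be hard to reconstruct later.

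Part of this stands. The proportion is not shown to estimate incidence in all non-cryptogenic stroke, and a report that presented it that way would overreach. A simple count of screened patients who missed the age or risk condition, where known, would be useful to readers.

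The rest does not make a defect in the plan. The introduction's sentence about changed management is conditional background and does not extend the result to patients outside the criteria. A protocol has no conclusions section in which such a limit would be expected. Other features also narrow the cohort without appearing in the objective, among them the single center, implantation within 10 days and the life-expectancy and anticoagulation exclusions. Counting patients excluded solely by age or risk would require every other criterion to be assessed in people who are never approached, including the work-up, implant timing and willingness to consent.

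**Conclusion.** The mismatch in wording is real, and no change to the plan follows from it. A one-sentence objective is narrowed by an eligibility list directly after it, as is common, and the denominator is defined as those studied. The estimate and its interval are valid for the enrolled group, and selecting patients at higher risk is a fair choice for a 75-patient implant study. Analysts will in the ordinary course report the proportion for patients meeting the stated criteria.

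No size can be given from the documents. The illustrated gaps of 1.0 to 10.5 points rest wholly on assumed values of f, pE and pI, and the gap is zero if all the wider population qualifies or the two risks are equal. The reading assumes that the result is reported for the cohort the eligibility section describes. Naming those limits beside the objective would be an editorial nicety with no effect on any analysis.

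### The Kaplan-Meier rule credits every AF-free patient with 12 months of follow-up, even when device monitoring ended earlier

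*Combined protocol and SAP*

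**What the plan says.** The Statistical Analysis section plans two descriptions of AF occurrence.

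- A crude incidence: the "total number of patients with AF in 12 months divided by the total number of patients studied", with a 95% confidence interval.
- A Kaplan-Meier analysis of time to first documented AF. Where AF "had not yet occurred, 12 months will be used and considered" censored. "The median rate will be obtained from the Kaplan-Meier/Product-Limit Estimates", with a confidence interval based on Greenwood's standard error.

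Three other places bear on the censoring rule.

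- **Design** plans "a minimum of 12 months of ICM monitoring" for each patient.
- **Follow Up** says "Device recording of an AF episode of at least 2 minute duration will be required to diagnose a patient with AF". It also provides for daily automatic downloads and says "Participants will be required to perform a manual device interrogation on a monthly basis".
- **Discontinuation of Study/Subject Withdrawal** says "Subjects have the right to withdraw from the study at any time without prejudice". It also lets the investigator "withdraw the subject from the study and remove the implantable device in the event of intercurrent illness" or for other listed reasons, and provides for withdrawal and device removal when a patient regains capacity and does not want the device.

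No section says how an AF-free patient with less than 12 months of monitoring enters the Kaplan-Meier analysis.

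**The concern.** Once the device is out or has stopped transmitting, AF can no longer be diagnosed under the protocol's definition. A patient who leaves at month 3 without AF contributes three months of information. The written rule records twelve, so nine unobserved months count as AF-free and the patient stays in the risk set throughout.

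Handling unequal observation time is the reason to use Kaplan-Meier here, and this is the only planned analysis that could do it. If nobody is censored before month 12, the curve at 12 months merely repeats the crude proportion. Any early exit for a reason other than death then pulls the curve down. At stake are the drawn curve, its pointwise standard errors and any 12-month value read from it.

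**Working it through.** The plan gives no figure to reproduce: no expected AF rate for this population, no dropout rate and no derivation of the sample size. The inputs taken from the documents are 75 patients, the 12-month rule, Kaplan-Meier and Greenwood. AF risk, exit rate and timing are assumptions, shown over a range.

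**1. What the rule does algebraically.** If only AF events leave the risk set before month 12, the Kaplan-Meier product telescopes. With d events in N patients and no ties:

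- S(12) = (N−1)/N × (N−2)/(N−1) × … × (N−d)/(N−d+1) = (N−d)/N, so 1 − S(12) = d/N.
- Greenwood's sum is Σ 1/[n(n−1)] = 1/(N−d) − 1/N. The variance is therefore S² × d/[N(N−d)] = (d/N)(1−d/N)/N, which is the binomial variance.

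Both results hold however many AF-free patients left early.

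**2. Expected size.** Let p be the true 12-month risk, F(t) the AF distribution over the year (time scaled to 0–1) and e the proportion with a non-death exit, uniform over the year and unrelated to AF. The expected as-written value is

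(1−e)·p + e·∫F(t)dt.

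For p = 20% and constant hazard, F(t) = 1 − 0.8^t and the integral is 0.1037. With AF concentrated early (Weibull shape 0.6), the integral is 0.1288.

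| Exit rate | Constant hazard | Early AF (shape 0.6) |
|---|---|---|
| 5% | 0.95×20 + 0.05×10.37 = 19.5% | 19.6% |
| 10% | 0.90×20 + 0.10×10.37 = 19.0% | 19.3% |
| 20% | 18.1% | 18.6% |
| 30% | 17.1% | 17.9% |

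The standard error at 20% and N = 75 is √(0.2×0.8/75) = 4.62 points. At 5–10% exit the shift of 0.5–1.0 point is thus about 0.1–0.2 of a standard error.

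**3. Worked example.** Take 75 implanted, 14 with AF and 8 AF-free early exits, none by death, with both sets of times at the midpoints of equal intervals over the year.

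- As written: 14/75 = 18.7%, SE √(0.1867×0.8133/75) = 4.50 points, log-log 95% CI 11.5–29.5%.
- Censored at actual exit: the numbers at risk at the 14 events are 75, 73, 72, 70, 68, 67, 65, 64, 62, 61, 59, 57, 56 and 54. The product of (1 − 1/n) is 0.8017, giving 19.8%, SE 4.76 points, CI 12.2–31.2%.

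**4. Deaths.** With death as a competing event, patients who die without AF properly stay in the denominator. If 2, 4, 6 or 8 of the 8 exits are deaths, the corrected value averages 19.5, 19.2, 18.9 or 18.7%. When all are deaths, the gap is zero.

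**5. The median.** It is reached only if the curve passes 50%. With full follow-up, the probability that at least 38 of 75 have AF is 3.2×10⁻⁹ at a 20% risk and 0.00014 at 30%. In 48,000 simulated cohorts (risk 10, 20 or 30%, exit 5–30%), the median was reached 0 times as written and 3 times with censoring at actual exit.

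**6. Interval coverage.** At a true 20%, with 5,000 simulated cohorts per exit rate, coverage was 95.3–96.5% as written and 95.0–95.6% with censoring at actual exit.

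**The case against.** The strongest reply is that the sentence was meant as an administrative cap. Monitoring is planned for at least 12 months, removal is planned at one year, and the text calls for conventional survival methods. On that reading, 12 months applies to completers and the plan is only silent on early leavers. That may well be the intent. But the sentence is the only censoring instruction, it is specific, and it covers all patients without AF. An analyst following it would enter 12 months.

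A second reply is that withdrawn patients might not be analysed at all, since the plan does not define who counts as studied. In that case the mechanism would not arise, but the plan does not say they are excluded, and dropping them would discard their monitored time.

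A third reply is that the correction does not clearly improve accuracy at this sample size. This is true for mean squared error. At a true 20%, root mean squared error as written against corrected is 4.59 against 4.67 points at 5% exit, 4.63 against 4.74 at 10% and 4.85 against 4.90 at 20%. The correction wins only at 30% exit (5.17 against 5.02). These differences are small, and the as-written advantage comes from an estimate that is biased low and treats unobserved time as observed. That is no reason to keep the rule, but it supports a low rating.

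It also stands that the planned crude incidence shares the same downward bias, and that no decision rule depends on the curve.

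**Conclusion.** The rule is wrong as written, and the consequence is minor. Taken literally, it makes the Kaplan-Meier curve ignore early loss of monitoring, so that the 12-month value and its standard error collapse to those of the crude proportion.

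The downward shift is about 0.5–1.0 point at 5–10% exit and 1.9–2.9 points at 20–30%. This assumes a true risk of 20%, constant hazard, and non-death exits uniform over the year and unrelated to AF. It is somewhat smaller if AF occurs early, and zero if everyone completes 12 months or if all early exits are deaths. The planned median and the separately calculated incidence are essentially untouched, and interval coverage is not lost. The exit rate is an assumption throughout.

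**What to change.** Replace the censoring sentence with: *Patients without AF are censored at the earlier of 12 months after implantation and the date of the last device transmission received (automatic or manual); death before AF is a competing event.*

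Keep the planned crude proportion as the incidence estimate, and state that its denominator is all implanted patients, which the plan leaves undefined. Beside it, report the 12-month cumulative incidence with its 95% CI, and the number, timing and reasons of early exits.

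**Cost.** One clause, plus one date per patient. The protocol does not say that transmission dates are kept, but the monthly manual interrogation would supply the date to within about a month. Rounding the eight exits in the example down to the month moves 19.8% only to 19.9%. The interval widens slightly (SE 4.50 to 4.76 points in the example).

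**Limit.** The correction assumes that exit is unrelated to AF. For an overall true risk of 20%:

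| Leavers' AF hazard | Exit rate | As written | Corrected |
|---|---|---|---|
| Half | 10% | 19.5% | 20.5% |
| Half | 20% | 18.9% | 21.0% |
| Double | 10% | 18.4% | 19.3% |
| Double | 20% | 17.1% | 18.7% |

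With half the hazard, the fix only reverses the sign of the error; with double, it helps. This is why the reasons for exit should be reported.
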